## 6. METHODOLOGY

**HLA antibody detection.** For assessment of the course of DSA levels, serum samples will be evaluated after completion of the study (part A and B). If detailed data on preformed DSA are not available, stored pre-transplant sera will be tested retrospectively for the presence or absence of DSA. Sera will be heat-inactivated to preclude complement-dependent in vitro artifacts (prozone phenomenon) and subjected to single-antigen flow-bead testing (LABscreen Single Antigen assays; One Lambda). Test results will be documented as mean fluorescence intensities, and MFI >1000 will be considered positive. Donor-specificity will be defined according to donor and recipient HLA typing results. Virtual panel-reactive antibody (PRA) levels will be calculated using specific software tools (<http://www.eurotransplant.eu>).

**Transplant biopsies.** Biopsies will be performed after exclusion of a coagulation disorder or platelet counts below 80%. Anticoagulants or inhibitors of thrombocyte aggregation will be transiently paused. The biopsy will be performed under local anaesthesia (lidocain) using ultrasound-guided percutaneous techniques (1-2 cores per biopsy, 16 gauge needle). After biopsy, patients will be monitored closely for 5 to 8 hours for any complications (serial blood pressure measurements, monitoring for hematuria, haemoglobin check 4 hours after biopsy). Histomorphology will be evaluated on paraffin-embedded sections applying standard methodology. For immunohistochemical C4d staining, we will use a polyclonal anti-C4d antibody (BI-RC4D, Biomedica; Vienna, Austria), and, following the rules of the Banff scheme , minimal immunohistochemical staining (C4d Banff score  $\geq 1$ ) along peritubular capillaries will be considered positive. Biopsies will in addition be evaluated by electron microscopy for detection of multilayering of peritubular capillary basement membranes (MLPTC). All biopsies will be analyzed using microarrays, as proposed by the Banff scheme.

For each biopsy, a 3 mm portion of one core will be placed immediately in RNAlater, stored at -20°C and shipped at ambient temperature or dry ice to the Alberta Transplant Applied Genomics Centre (ATAGC, University of Alberta, Edmonton, AB, Canada) for gene array analysis. Thoroughly validated molecular scores based on machine-learning derived lesion-based classifiers related to rejection (ABMRpm, TCMRt, all Rejection) will be generated using the Edmonton reference set of >1200 biopsies. Moreover, gene expression patterns will be evaluated using unbiased archetype analysis. Morphological results will be evaluated by experienced renal transplant pathologists blinded for treatment allocation. For classification of ABMR according to the Banff 2013 scheme, all biopsy results will be analyzed in the context of the molecular results. ABMR categories and morphological single lesions will be defined and scored following the 2013/2015 update of the Banff classification. ABMR will be defined on the basis of both morphological (histomorphology, immunohistochemistry, electron microscopy) and thoroughly validated molecular criteria: (i) evidence of acute or chronic tissue injury, (ii) evidence of current/recent antibody interaction with the vascular endothelium, and (iii) serological evidence of DSA.

**Kidney function.** eGFR will be assessed using the CKD-EPI formula. Protein excretion will be documented as protein/creatinine ratio.

**Pantoprazole pharmacokinetics** will be determined by liquid chromatography tandem mass spectrometry.

**Cytokine and markers of endothelial activation/injury.** Sera collected at week 0, 12 and 52 will be analysed for IL-6, soluble IL-6 receptor, soluble VCAM-1, soluble P-Selectin and DARC in order to document IL-6 decrease in the clazakizumab arm and to monitor endothelial activation and injury. Analysis will be carried out on FlowELISA beads in a multiplex approach (where possible) in a Luminex 200 or ELISA technology (DARC). In parallel, markers of inflammation and endothelial cell activation will be evaluated in urine.

**Leukocyte subpopulations.** The underlying mechanisms of chronic antibody mediated rejection, especially the role of peripheral T- and B-cell subsets are not fully clarified. Thus, the prospective monitoring of immune phenotype under therapy with clazakizumab is a promising approach to further elucidate the impact on immune-regulatory pathways when IL-6 signal is blocked. For monitoring of leukocyte (sub)populations we will use reproducible immune monitoring (IM) panels for phenotyping. Recently, the international "The ONE study" consortium has designed a standardized panel (DuraClone®) for flow cytometry based immune phenotyping that demonstrated robust results. In the DuraClone IM kits pre-

defined assay tubes contain a layer with the dried-down antibody panel ready to use. Up to 10 different monoclonal antibodies per tube allows the identification of leukocyte (e.g. T cell, B cell, NK cell subsets) subpopulations present in whole blood samples.

**Gene expression analysis.** For gene expression analysis, 5 mL of blood will be collected in PAXgene Blood RNA tubes and stored at -80°C until retrospective analysis. These tubes are designed for stabilization of RNA in blood during long-term storage at ultra-low temperature. After thawing, RNA will be isolated and transcribed into cDNA. The amount of RNA/cDNA of IL-6 or IL-6R will be determined by quantitative real-time-PCR using the TaqMan assay. Thereby, - on top of a common PCR reaction (amplification of template cDNA between two primer sequences by a DNA polymerase) - IL-6 or IL-6R-specific probes will be placed between the two PCR primers. These probes will be labelled with a fluorochrome which is released upon polymerase action. This released fluorochrome will be measured and compared to another fluorochrome that is released in parallel from a house-keeping gene like G3PDH.

**Torque Teno virus (TTV) quantification.** TTV DNA will be quantified retrospectively in stored plasma samples obtained at week 0, 12 and 52 using real time PCR.

**Collection of biological material (outside routine monitoring).** Plasma (10 mL; cytokines, endothelial markers, TTV load), serum (10 mL; HLA antibodies, cytokines, endothelial markers), whole blood (10 mL; flow cytometry, RNA for gene expression analysis) and urine (10 mL) will be collected before study initiation (day 0), after 12 and after 52 weeks (3x25 mL peripheral blood). For pantoprazole kinetics, peripheral blood samples will be collected serially (6 x 5 mL per day) at day 0, week 12 and week 52, respectively. Finally, for measurement of clazakizumab concentrations and anti-clazakizumab reactivity, serum will be obtained at every study visit (5 mL peripheral blood per visit; total of 17 visits). Biological material will be aliquoted and stored for testing (clazakizumab concentration, anti-clazakizumab antibody detection, HLA antibody detection, detection of cytokines and endothelial markers, TTV quantification) at the Department of Clinical Pharmacology.

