## **3. STUDY DESIGN**

This bi-center study (MUW, Charité Berlin) is an investigator-driven pilot trial designed to assess the safety, tolerability, pharmacokinetics, pharmacodynamics and efficacy (preliminary assessment) of humanized anti-IL-6 monoclonal antibody clazakizumab in kidney transplant recipients with late ABMR. This study, a phase 2 trial, has two subsequent sub-parts, a randomized placebo-controlled trial (part A) of 12 weeks, where recipients are allocated to receive either clazakizumab (n=10) or placebo (n=10), followed by an open-label prospective study, where all 20 study patients will receive clazakizumab for a period of 40

weeks. In this second part, treatment will be offered to all subjects for two major reasons: (i) in a recent uncontrolled preliminary observational study, interference with IL-6/IL-6R blockade in ABMR patients using tocilizumab was reported to be safe and well tolerated, and first results have suggested stabilization of kidney function in many of the treated patients; (ii) two subsequent protocol biopsies planned in our trial, which are necessary for an in-depth analysis of the early and late effects of IL-6 blockade, would not be justified for long-term placebo treatment. After completion of part A, the randomization sequence will be unblinded for a first analysis of data. A simplified flow chart of the trial is shown in Figure 1:

Figure 1. Trial overview

**Part A:** Patients will be randomized to receive either clazakizumab (25 mg subcutaneous [SC] administration) or placebo (1:1 randomization) for a period of 12 weeks (administration of clazakizumab/placebo at day 0, and after 4 and 8 weeks). After 12 weeks, patients will be subjected to a first follow-up biopsy. Primary goals of this part of the trial are to assess the safety, pharmacokinetics and pharmacodynamics of a short course of treatment. Moreover, part A will allow for a first preliminary assessment of the impact of clazakizumab on ABMR-associated inflammation detected in peripheral blood and in the rejecting organ allograft, on the pharmacokinetics of pantoprazole as a probe drug to investigate influence of IL-6 blockade on cytochrome P450-dependent drug metabolism, and on the short-term course of DSA MFI and kidney allograft function (eGFR, urinary protein excretion). The randomization

sequence will be unblinded for a first data analysis after the last patient has completed the 12-week follow-up period.

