**Primary and secondary outcomes in part A and part B of the trial**

PRIMARY OUTCOME
Safety and tolerability
SECONDARY OUTCOMES (PART A AND B)
PK of clazakizumab (every visit; measurement of anti-Claza antibodies included) and of pantoprazole (0, 12, 52 weeks)

PK/PD of clazakizumab (clazakizumab levels and CRP suppression) (every visit)  
Cytokines patterns and endothelial activation/injury markers in serum (0, 12, 52 weeks)  
Effect on leukocyte subsets in peripheral blood  
Effect on IL-6 and IL-6R gene expression in peripheral blood cells  
HLA antibody levels (0, 12, 52 weeks)  
    Maximum and sum of mean fluorescence intensity (MFI) of DSA  
    Number of DSA  
    Broadness of sensitization (virtual PRA)  
Total Ig classes (IgG, IgA, IgM) and IgG subclasses (IgG1, 2, 3, 4)  
Protocol biopsy results at 11 and 51 weeks  
    ABMR category  
    Microcirculation inflammation (g+ptc score)  
    Transplant glomerulopathy (cg) and interstitial fibrosis/tubular atrophy (IFTA) scores  
    Molecular ABMR score (molecular microscope, MMDx)  
    Archetype analysis of gene expression profiles (molecular microscope, MMDx)  
eGFR (every visit)  
Protein excretion (protein/creatinine ratio) (every visit)  
1-year graft and patient survival  
Occurrence of biopsy-proven acute rejection necessitating rejection treatment (52 weeks)

The schedule of events is provided in Table 3.

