immunosuppression, can be expected to be associated with an increased infection risk. Hence, a careful patient follow-up will include a close monitoring for infectious complications (bacterial, viral and fungal infections). In trials of arthritis, no case of gastrointestinal perforation was reported. However, given the low, but significantly increased risk of gastrointestinal perforation in other large studies evaluating IL-6/IL-6R blockers, patients with a history of gastrointestinal perforation, diverticulitis or inflammatory bowel disease will not be included in the trial. Clazakizumab, as other agents interfering with IL-6/IL-6R, was shown to increase total cholesterol and LDL levels. Moreover, in some patients, a mild decrease in platelet counts was observed. Serious infusion reactions have not been described in any of the published trials, but clazakizumab may cause injection site reactions, apparently in a dose-dependent fashion. Safety results obtained for prolonged treatment with subcutaneous clazakizumab at 25 mg (with or without methotrexate) in two recent phase 2 trials, one in RA, the other in PsA, are summarized in Table 5 (in both trials also higher doses of clazakizumab were evaluated; some events, such as injection site reactions or liver enzyme elevations, were thereby more frequently observed at higher dosages).

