**Hematologic Abnormalities and Bleeding Events**

Decreases in neutrophil and platelet counts have been observed following treatment with clazakizumab in combination with MTX. In addition, there may be an increased risk of neutropenia in patients who have previously been treated with a TNF antagonist. For patients with concomitant medications associated with hematologic toxicity, the reduction or interruption of the suspected medication is recommended prior to modifying clazakizumab. Dosing guidance for neutropenia and thrombocytopenia are described in Tables 6 and 7.

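### Soluble P-selectin is measured in serum and read as an endothelial marker, so a platelet fall on clazakizumab can lower it without any endothelial change; platelet-poor plasma with stated handling would remove most of this at little cost

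*Combined protocol and SAP*

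**What the plan says.** - **Matrix and purpose.** Section 6, in its paragraph on cytokine and endothelial assays: "Sera collected at week 0, 12 and 52 will be analysed for IL-6, soluble IL-6 receptor, soluble VCAM-1, soluble P-Selectin and DARC". Besides documenting an IL-6 decrease, the stated aim is "to monitor endothelial activation and injury".
- **Outcome status.** The Section 5 outcome table lists, as a secondary outcome for parts A and B: "Cytokines patterns and endothelial activation/injury markers in serum (0, 12, 52 weeks"). The text of Section 5 places these markers under preliminary efficacy assessment.
- **Samples drawn.** Section 6, under collection of biological material, lists for day 0, week 12 and week 52: "Plasma (10 mL; cytokines, endothelial markers, TTV load), serum (10 mL; HLA antibodies, cytokines, endothelial markers"). No anticoagulant, clotting time, centrifugation or platelet-removal step is given.
- **Platelets on drug.** Section 9, under Clazakizumab: "in some patients, a mild decrease in platelet counts was observed". Section 9, under hematologic abnormalities: "Decreases in neutrophil and platelet counts have been observed following treatment with clazakizumab in combination with MTX". Neither place gives a size, and Table 5 has no platelet row.
- **Comparison.** In part A "recipients are allocated to receive either clazakizumab (n=10) or placebo (n=10"). Section 7 plans two-group and paired tests for continuous data and mentions no adjustment for platelet count.

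**The concern.** Platelets as well as endothelium contain P-selectin, and making serum means letting the platelets in the tube activate. The assay therefore returns the circulating amount plus an amount released after the blood was drawn, and the second part depends on how many platelets were in the tube.

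If clazakizumab lowers platelets, the second part falls with treatment. Randomisation and blinding do not protect against this, because the platelet fall would itself be a treatment effect. At week 52 there is no concurrent placebo group. Patients first given placebo start clazakizumab at week 12, so their change from week 12 to week 52 could carry the same artefact and look like independent confirmation of part A.

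What is at stake is interpretation. A lower P-selectin on drug could be reported as less endothelial injury when it partly reflects platelet count, in a pilot whose stated use is to inform later trials. The primary safety outcome is not touched.

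**Working it through.** The protocol states no effect, variability or sample size for P-selectin, so there is no figure to reproduce. The check has two parts.

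**1. The links in the argument**

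| Link | Source | Supported? |
|---|---|---|
| P-selectin assayed in serum | Section 5 outcome table; Section 6 | Yes |
| Read as endothelial activation/injury | Sections 5 and 6 | Yes |
| Clotting platelets release P-selectin | Not in the documents | General laboratory knowledge |
| Clazakizumab can lower platelets | Section 9, two places | Yes, but mild, in some patients, partly with methotrexate; no size |
| Plasma drawn at the same visits | Section 6, collection of material | Yes |
| That plasma is platelet-poor | Not stated | Not shown |

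**2. Size under stated assumptions**

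Let f be the share of serum P-selectin released by platelets in the tube, and d the mean relative platelet fall on drug. If tube release is proportional to platelet count and the circulating part is unchanged, the apparent fall is f × d. Both inputs are assumptions.

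| f | d = 10% | d = 20% |
|---|---|---|
| 0.3 | 3% | 6% |
| 0.5 | 5% | 10% |
| 0.7 | 7% | 14% |

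Wider assumptions (f from 0.25 to 0.75, d from 5% to 30%) give 0.25 × 5% = 1.3% up to 0.75 × 30% = 22.5%. If f is close to 0, as intended with platelet-poor plasma, the tube artefact is close to 0 whatever d is.

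**Could the artefact alone look like an effect at 10 per arm?** Work on the log scale with a two-sided 5% level and an assumed log-scale SD s:

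chance of p<0.05 in the favourable direction = Φ( −ln(1 − f·d) / (s·√(2/10)) − 1.96 )

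| Apparent fall | s = 0.2 | s = 0.35 | s = 0.5 |
|---|---|---|---|
| 3% | 5% | 4% | 3% |
| 5% | 8% | 5% | 4% |
| 10% | 22% | 10% | 7% |
| 14% | 39% | 16% | 10% |

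Example, 14% fall at s = 0.2: −ln(0.86) = 0.151; 0.2 × 0.447 = 0.0894; 0.151/0.0894 = 1.69; Φ(1.69 − 1.96) is about 0.39. With no artefact the chance in that direction is 2.5%.

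Under the wider assumptions, a platelet fall of 10% or less gives 3-14%. The extreme corner (f = 0.75, d = 30%, s = 0.2) gives 81%.

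For scale, the difference detectable with 80% power is (1.96 + 0.84) × √(2/10) = 1.25 SD. That is a fall of 1 − exp(−1.25 × 0.2), about 22%, at s = 0.2, and 1 − exp(−1.25 × 0.5), about 47%, at s = 0.5. An artefact of 3-14% is below both.

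**Plasma volume.** The blood samples listed in Section 6 sum to 10 + 10 + 10 = 30 mL per time point, against the stated 25 mL. How much plasma is available needs confirming before another assay is assigned to it.

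**The case against.** The case for leaving this alone is substantial.

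- **No quantity comes from the trial.** The release mechanism is outside knowledge, and the platelet share, platelet fall and SD are all assumed. This stands: the size cannot be derived, only illustrated.
- **The platelet premise is soft.** Section 9 reports a mild fall in some patients, and one of its two statements ties the falls to methotrexate, which is not among the immunosuppressants that Section 4 lists as permitted. This stands too. A mean fall of 10-20% is not established for this population.
- **A reader might infer that the part A comparison is biased towards benefit.** The documents do not support that. They support only that it can be, if platelets fall on drug in this trial.
- **A reader might infer that a suitable sample is already in the freezer.** Plasma is drawn, but without a stated anticoagulant or platelet-removal step its suitability is unproven.
- **A reader might infer that the protocol contradicts itself on the matrix.** That is too strong. Sections 5 and 6 agree on serum for the assay. The collection list reserves both matrices for endothelial markers generally and does not assign P-selectin to plasma. The wording should be aligned, no more.
- **Some protection exists.** A safety laboratory is scheduled at weeks 0, 12 and 52, and Table 7 presupposes platelet counts, so these should be available. Soluble VCAM-1, DARC and urine markers are also measured. This lowers the stakes, but nothing in the plan says that P-selectin will be read against the platelet count.

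The mechanism itself is left standing: a serum value cannot separate endothelial change from platelet change, and the randomised comparison does not separate them either.

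**Conclusion.** The point holds in a limited form. Serum P-selectin can fall because platelets fall, and the plan would read that as less endothelial activation or injury. The direction is towards apparent benefit. The size is not derivable from the documents. Under the assumed 30-70% platelet share and 10-20% platelet fall it is about 3-14%, which is probably modest unless the platelet fall is large. It would seldom reach significance alone when platelets fall by 10% or less.

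The conclusion rests on general laboratory knowledge about platelet release, on tube release proportional to platelet count, and on the platelet effect in Section 9 carrying over to these patients. It concerns one exploratory marker within a secondary outcome. It is a worthwhile low-cost improvement, not a flaw that threatens the trial's main conclusions.

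**What to change.** 1. In Section 6, and in the matching line of the Section 5 outcome table, name plasma as the matrix for soluble P-selectin at weeks 0, 12 and 52. Changing Section 6 alone would leave it in conflict with the outcome table.
2. State that this is platelet-poor plasma, with one anticoagulant and one centrifugation procedure used at both centres and all visits.
3. Report the same-visit platelet count beside the P-selectin result.
4. If only serum can be used, label the result platelet-dependent and do not interpret it as endothelial injury.
5. Reconcile the 30 mL of listed blood samples with the stated 25 mL per time point, and confirm that the plasma volume suffices.

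Cost: short wording changes in two sections, a handling instruction for the centres, and possibly a separate bead run for this analyte. No extra visit is needed, and no extra draw if the plasma volume proves sufficient.

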## 7. SAMPLE SIZE AND STATISTICAL ANALYSIS

For this pilot study, no exact sample size estimation can be performed, because the effect size is unknown (there is no prior information to base a sample size on). The primary endpoint will be safety and tolerability. A preliminary assessment of efficacy outcomes in 20

kidney transplant recipients with late ABMR will provide first data on the effect of clazakizumab on clinical, morphological, immunological and molecular endpoints. The respective results (e.g. comparison between clazakizumab and placebo with respect to microcirculation inflammation and molecular rejection scores; course of chronic injury from 3 to 12 months), including an assessment of variability, can be expected to provide a valuable foundation of the design of future trials. Analyses will be conducted according to the intention-to-treat principle. Continuous data (e.g. group comparisons in part A for DSA-MFI, g+ptc score, IF/TA score, molecular ABMR score, eGFR and protein/creatinine ratio after 3 months) will be analysed using parametric and non-parametric (independent/dependent data) tests. These include the Mann Whitney U test or the t-test, as appropriate. Nominal data (e.g. occurrence of AEs in the two treatment groups in part A of the study) will be compared using the Fisher's exact test, when appropriate. Transplant and patient survival or AE (SAE)-free survival will be evaluated using Kaplan Meier analysis and the log rank test will be applied for group comparisons. For paired data (e.g. difference in IF/TA score between month 3 and month 12 in the overall cohort - part B), paired t test or Wilcoxon test will be used as appropriate. Analysis of pharmacokinetics of clazakizumab and pantoprazol will include a description of the time evolution of antibody/drug concentration. Elimination half-life, Tmax, Cmax, clearance and volume of distribution will be computed using standard software. For some study endpoints, data on variability and center (median) that can be expected also for the present study, are available from a recent interventional randomized controlled trial performed at our unit, which included a similar cohort of kidney transplant recipients diagnosed with late ABMR (BORTEJECT, NCT01873157; unpublished data; protocol described in: Eskandary et al., *Trials*. 2014 Apr 3;15:107). The respective data obtained in study groups are listed in the table below:

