This 12-month pilot trial is primarily designed to evaluate the safety, tolerability, pharmacokinetics and pharmacodynamics of clazakizumab versus placebo in a cohort of 20 kidney transplant recipients diagnosed with late ABMR. The design of the study, which includes early and late follow-up protocol biopsies to decipher the effects on microcirculation inflammation, gene expression profiles and features of chronic transplant injury will also allow for preliminary efficacy assessment (information on effect size and variability), and thus can be expected to provide a valuable foundation of future trials in large populations of transplant patients.

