### **Inclusion/exclusion criteria**

We will include kidney transplant recipients with circulating anti-HLA DSA and biopsy features of ABMR (ABMR according to the Banff 2013 scheme) in an indication biopsy (index biopsy; performed for a positive post-transplant DSA result and/or slow deterioration of allograft function and/or proteinuria. Other key inclusion criteria are a functioning graft at  $\geq 365$  days post-transplantation and an eGFR above 30 ml/min/1.73 m^2. This eGFR threshold has been chosen to avoid inclusion of transplants with a high degree of irreversible chronic damage (for patients with very advanced graft injury a sustainable treatment benefit can no longer be expected). Inclusion and exclusion criteria are listed in Table 1.

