### **Random allocation**

For part A of the trial, patients will be centrally randomized by computer assignment between two study arms (part A of the study: clazakizumab versus placebo) using <http://www.randomization.com> (1:1 randomization). Stratification according to acute/active ABMR and chronic/active ABMR will be used to ensure a balance of patients with these two histological types between the two arms. For each patient, a study ID will be assigned. The participating investigators and the patients will be blinded to group allocation until the completion of part A of the study.

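### Section 7 prespecifies neither the week-0 value nor the randomisation stratum for the part A comparisons of eGFR, DSA MFI and proteinuria; adding both is a cheap, low-severity gain in precision

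*Combined protocol and SAP*

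**What the plan says.** Section 7 lists, as examples, "group comparisons in part A for DSA-MFI, g+ptc score, IF/TA score, molecular ABMR score, eGFR and protein/creatinine ratio after 3 months". These are to be analysed with "parametric and non-parametric (independent/dependent data) tests", and the next sentence reads "These include the Mann Whitney U test or the t-test, as appropriate". The paired tests are illustrated by month 3 against month 12 in the whole cohort, which is not a comparison between arms.

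Under Random allocation, section 3 states: "Stratification according to acute/active ABMR and chronic/active ABMR will be used to ensure a balance". Nothing elsewhere in the document carries that stratum into an analysis.

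The schedule of events (Table 3) collects DSA, eGFR and protein/creatinine ratio at weeks 0 and 12. Biopsies are scheduled only at weeks 11 and 51, so the one pre-treatment biopsy is the qualifying one, described as found "in an indication biopsy (index biopsy; performed for a positive post-transplant DSA result" or for other clinical reasons. No interval from that biopsy to day 0 is fixed.

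Section 1 gives the purpose of the efficacy part as "preliminary efficacy assessment (information on effect size and variability"). Section 7 adds that the results, "including an assessment of variability, can be expected to provide a valuable foundation of the design of future trials".

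**The concern.** With 10 patients per arm, between-patient spread dominates any comparison of follow-up values. Where the week-0 value predicts the week-12 value, conditioning on it removes part of that spread at no cost in visits or samples. A plan that collects the value but does not commit to using it risks wider intervals than the data allow. It may also not yield the residual SD and the baseline to follow-up correlation that a later trial would need for planning.

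Prespecification matters because the code is opened for a first analysis once the last patient completes week 12. A covariate chosen after that point could be challenged as data-driven.

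**Working it through.** **Inputs from the documents.** 10 patients per arm (section 3). Entry limits in Table 1: eGFR above 30, and protein/creatinine ratio above 3500 mg/g excluded. HLA antibodies must be detected (Table 1), and MFI above 1000 counts as positive (section 6). Spread from Table 4, all patients: eGFR 44 (23-72; 15-95), immunodominant DSA 3553 (1012-10365; 163-16284), protein/creatinine ratio 201 (86-1249; 0-4863).

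**Assumptions.** Two-sided 5% level; r from 0 to 0.9; Table 4, which has no legend, read as median (quartiles; range). There is no power or sample-size figure to reproduce.

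**Unadjusted reference.** The 95% CI half-width is t(18 df) x sqrt(2/10) = 2.101 x 0.447 = 0.94 SD.

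**Adjusted, no entry restriction, stratum balanced across arms.** The variance ratio to the unadjusted analysis is (1 - r^2) x (1 + 1/15). The half-width ratio is the square root of that, times t(16)/t(18) = 2.120/2.101 = 1.009.

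| r | variance ratio | half-width ratio |
|---|---|---|
| 0 | 1.067 | 1.04 |
| 0.3 | 0.971 | 0.99 |
| 0.5 | 0.800 | 0.90 |
| 0.7 | 0.544 | 0.74 |
| 0.9 | 0.203 | 0.45 |

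With an unbalanced stratum the inflation factor is 17/15 in place of 16/15. At r = 0 the half-width ratio is then sqrt(1.133) x 1.009 = 1.07. Break-even solves (1 - r^2) x inflation x 1.009^2 = 1, which gives r = 0.28 (balanced) and 0.37 (unbalanced).

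Simulated power for a 1 SD effect, unadjusted against adjusted, is 55% v 65% at r = 0.5 and 56% v 81% at r = 0.7.

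**With the entry limits.** Baseline and follow-up are given the Table 4 distribution, linked by a Gaussian copula with latent correlation r, and only patients meeting the limit at baseline are kept. DSA and protein/creatinine ratio are on the log scale. The DSA cut at MFI 1000 and a protein/creatinine minimum of 10, needed for the log, are assumptions. Repeated simulations differ by a few points, so ranges are shown for the share of unadjusted variance remaining.

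| latent r | eGFR (>30) | maximum DSA MFI (1000 or more) | protein/creatinine (up to 3500) |
|---|---|---|---|
| 0.3 | 103% | 102-104% | 98-99% |
| 0.5 | 94-97% | 94-95% | 86-88% |
| 0.7 | 78% | 78-79% | 63-67% |
| 0.9 | 42-47% | 42-44% | 27-30% |

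Cross-check for eGFR: the cut at 30 lowers a latent r of 0.7 to about 0.52 among those enrolled, and (1 - 0.52^2) x 1.067 = 0.78. Summed DSA MFI behaves similarly to the maximum: about 102%, 92%, 74% and 38%.

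**Stratum term.** If ABMR type shifts the outcome by 1 SD (assumption), the stratum term alone cuts the half-width from 1.05 to 0.93 SD. With no stratum effect it widens the interval by about 1%.

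**The case against.** The primary outcome is safety and tolerability, no power is claimed, and the unadjusted tests are valid. That stands, and it limits the point to low severity.

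The wording is also open. The endpoint list is introduced as an example, the test list is not closed, and section 3 speaks of the "short-term course of DSA MFI and kidney allograft function (eGFR, urinary protein excretion"), which could cover a change analysis. A reader might infer that the plan excludes adjustment. It does not; it only fails to prespecify it.

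A reader might also infer that ignoring the stratum makes the test invalid. It does not: with a 1 SD stratum effect the simulated type I error of the unadjusted t-test is about 2.7% to 2.9%, which is conservative. No section says that histological type is prognostic for these outcomes.

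Section 5 says that the week-11 biopsy is mainly for microcirculation inflammation, so it is tempting to extend adjustment to g+ptc, IF/TA and the molecular score. The documents do not support that. The only baseline is an untimed index biopsy, possibly taken before the immunosuppression adjustment in section 4, and the molecular score must be at least 0.2 at entry. In an illustrative simulation for g+ptc (assumed 1 SD latent shift), stratified rank ANCOVA had 44% power against 48% for Mann-Whitney at r = 0, and 46% against 48% at r = 0.3. The gain is uncertain and may be negative.

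Finally, all sizes depend on an undocumented r. Absolute eGFR figures are especially soft. The spread in Table 4 gives an SD of about 25 if the range is respected, but (72 - 23)/1.349 = 36 by normal theory.

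**Conclusion.** The point holds as a low-severity, inexpensive improvement for the three endpoints with a week-0 laboratory value. Nearly all the gain comes from the baseline value. The stratum term mainly aligns the analysis with the randomisation.

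The size is conditional. Without entry restriction, about 54% of the variance remains at r = 0.7. Under the illustrative entry limits, about 78% remains for eGFR and for maximum DSA MFI, and about two thirds for protein/creatinine ratio. At r = 0.3 there is little or nothing to gain. Break-even is r of about 0.3 to 0.4, and somewhat higher under entry restriction. That r is high enough over 12 weeks is plausible, most of all for eGFR, but it is not documented. The unrestricted figures should not be read as applying to all three endpoints.

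**What to change.** In section 7, before the part A code is opened:

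- Prespecify for eGFR, DSA MFI and protein/creatinine ratio an ANCOVA of the week-12 value on arm, week-0 value and ABMR stratum.
- Use a log scale for DSA MFI and protein/creatinine ratio, with a stated rule for zeros (Table 4 shows ratios of 0).
- Name which DSA measure, maximum or sum, is analysed; the outcome list in section 5 has both.
- Drop the stratum term if a stratum is too small to estimate; neither stratum shares nor block size is given.
- Report adjusted differences with 95% CIs, residual SDs and observed baseline to follow-up correlations.
- Keep the unadjusted tests as sensitivity analyses.
- Leave g+ptc, IF/TA and the molecular score as planned.

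The cost is a few sentences and two degrees of freedom (18 to 16), plus the slight widening shown above if baseline turns out to be uninformative. No extra visits, samples or patients are needed.
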